3.7 Safety Analysis

3.7.1 Primary Safety Analysis

The primary safety analysis of the serious adverse events will be based on the cSAF. The rate of serious adverse events during and after enteroscopy procedure will be computed as the number of such serious adverse events divided by the number of patients in the cSAF. A 95% Clopper-Pearson confidence interval will be computed for the rate to assess the variability of the estimate. In case of an upper 95% confidence limit von 8% or below, non-inferiority to preceding generations of balloon assisted enteroscopes will be concluded.

The primary endpoint will be assessed in the core SAF as primary analysis. As secondary analyses, the primary endpoint will be assessed for the SAF, ITT and core ITT as well as for training patients only.

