Clinical Investigation Plan

CIP Reference No.:2018-GI (OEKG) -01. The **SAMISEN** study - Final Version 02 - Date 23th April 2019

The main objective of the SAMISEN study is to assess the performance and safety of diagnostic and therapeutic procedures with the newly designed Olympus Motorized Spiral Enteroscope (INTESTINAL VIDEOSCOPE OLYMPUS PSF-1 and SINGLE USE POWERSPIRAL TUBE DPST-1) system in combination with the motor control unit (POWER SPIRAL CONTROL UNIT PSCU). All Serious Adverse Events (SAE) observed in this study will be documented so the overall SAE rate as well as the number of individual types of complications (bleeding, pancreatitis etc.) can be calculated.

The very recent publication of Rondonotti (Rondonotti et al. 2018) for device-assisted enteroscopy for diagnosis and treatment of small-bowel disorders represents an excellent source for comparison. Hence this study is designed as a prospective study without control group. The resulting SAE rate will be compared to the historical data from this ESGE Technical Review (Rondonotti et al. 2018).

The performance will be characterized by calculating the Diagnostic and Therapeutic Yield, Total Procedure Time, time needed for Therapeutic Intervention, Total Small Bowel Enteroscopy Rate and user feedback on device handling.

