3.1.2 Randomization and Blinding or Assignment of Investigational Device

SAMISEN is designed as a prospective single-arm trial without control group or randomization. All subjects enrolled will undergo at least one procedure with the Motorized Spiral Endoscope (PowerSpiral). There may be a second (optional) procedure depending on investigator's discretion usually because the region of interest could not be reached during the first endoscopy. Subsequent endoscopic procedures are often characterized by a switch in direction (a first antegrade route may be followed by a second retrograde approach or vice versa). From a study perspective and because only part of the subjects will receive a second procedure this additional procedure is called "optional" to indicate that it is not required by protocol but will only be performed if considered necessary by the treating investigator.

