3.1.3 Variables in the Clinical Investigation

It is a prospective and observational Registry without any additional procedure beyond clinical practice. The small-bowel enteroscopy has to be performed according the medical standard. Serious Adverse Events (SAE) and Device Deficiencies (DD) must be documented.

The main safety endpoint is a combined one, capturing all SAEs / DDs captured during the study period. The definition is:

- **Safety:** Incidence (% of subjects) and frequency (no. of subjects) of device or procedure related Serious Adverse Events (SAEs) and Device Deficiencies (DD) observed during/after the procedure.

As main efficacy endpoint we will determine in how many cases the suspected anatomical target lesion can be reached. The definition is:

- **Diagnostic Yield:** Defined as the percentage of procedures that either confirmed a diagnosis from previous studies, or established a new definitive diagnosis at the anatomical location identified in previous studies or findings that could explain the clinical symptoms (Sethi et al. 2014; Prachayakul et al. 2013; Lenz, Roggel, and Domagk 2013; Sanaka et al. 2012).

Clinical Investigation Plan

CIP Reference No.:2018-GI (OEKG) -01. The **SAMISEN** study - Final Version 02 - Date 23th April 2019

Further efficacy endpoints cover performance aspects of the device. The definitions are:

- **Therapeutic Yield:** Defined as the percentage of patients with any endoscopic intervention / therapy with the exception of biopsies. (Sethi et al. 2014; Prachayakul et al. 2013; Sanaka et al. 2012).
- **Total procedure time:** the time from oral (anal) insertion until withdrawal of the device.
- **Total therapeutic intervention time:** The part of the procedure dedicated to therapeutic maneuvers (biopsies will not be considered here).
- **Total small bowel enteroscopy rate:** Defined as complete evaluation of the small bowel either with a single approach or combined anterograde and retrograde approach (if complete small bowel enteroscopy is intended anyway (Committee et al. 2015; Gerson et al. 2015).
- **User feedback** and judgment of handling characteristics and other aspects.

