3.3.6 Sample size

A total of 260 subjects shall be enrolled into this registry. This number factors in an expected drop-out-rate of 5%. Taking into account a drop-out-rate of 5% data from a total of 245 patients is expected to be available for statistical endpoints analyses.

With a sample size of 245 patients, the SAE rate can be estimated with a precision (i.e. width of the 95% confidence interval for the SAE rate) as shown in the following table.

Clinical Investigation Plan

CIP Reference No.:2018-GI (OEKG) -01. The **SAMISEN** study - Final Version 02 - Date 23th April 2019

Table 1 Precision of estimations of the rate of patients with at least one SAE

Sample size N	Patients with SAE	Rate of patients with SAE	95% CI (Clopper- Pearson)
245	5	2.0%	0.7% - 4.7%
245	10	4.1%	2.0% - 7.4%
245	15	6.1%	3.5% - 9.9%
245	20	8.2%	5.1% - 12.3%
245	25	10.2%	6.7% - 14.7%
245	30	12.2%	8.4% - 17.0%

As historical control, a SAE rate of 8% is considered (upper limit of the accepted SAE rate for patients undergoing deep enteroscopy according to the guideline (Rondonotti et al. 2018)).

In addition, to reflect the learning curve of each individual investigator, the first 5 patients per investigator will be considered training patients to become familiar with the handling and usage. All information of these “training patients” will be documented in the eCRF. These will be analyzed separately. 12 clinical sites in Germany, Belgium, France, Netherland, Italy, Denmark, Norway and Finland will be approached. At each site there will be either one or two investigators. Based on current information there will be approx. 15 investigators participating. Adding patients from the learning curve ($15 \times 5 = 75$) and the 260 study patient’s counting towards the endpoints together this study will enroll approximately 335 patients in total.

The enrolment period starts in May/June 2019 and will stop once the expected number of patients per site is reached. This “Last-Patient-In” (end of recruitment) is expected in May/June 2020.

Each site with two investigators shall take every effort to enroll a balanced number of patients per investigator.

Statistical Analyses will be performed with SAS software version 9.4 (SAS Institute Inc., Cary, NC, USA).

Clinical Investigation Plan

CIP Reference No.:2018-GI (OEKG) -01. The **SAMISEN** study - Final Version 02 - Date 23th April 2019

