2.2 Flow chart of study activities

2.3 Study Objectives

The primary endpoint of this study is the assessment of the rate of serious adverse events to show a non-inferiority to preceding generations of balloon assisted enteroscopes. Thus, the observed rate of serious adverse events will be computed alongside it's 95% Clopper-Pearson confidence interval. If the upper confidence limit will be 8% or less, non-inferiority will be concluded.

Secondary objectives are the description of the following parameters:

- Reaching the anatomical region of interest
- Therapeutic yield
- Total procedure time
- Total small bowel enteroscopy rate
- User feedback
- Safety profile
- Effect of the learning curve

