2.4 Primary and secondary variables

Primary efficacy variable:

The rate of serious adverse events during and after enteroscopy will constitute the primary endpoint for this study.

Secondary efficacy variables:

- Reaching the anatomical region of interest: The rate of successfully reaching the suspected anatomical target region (either by antegrade or by retrograde route) compared to all attempts represents the endpoint 'anatomical success rate'.
- Therapeutic yield: Defined as the percentage of patients with any endoscopic intervention / therapy with the exception of biopsies. (Sethi et al. 2014; Prachayakul et al. 2013; Sanaka et al. 2012)
- Total procedure time: Period in minutes needed to complete the procedure.
- Total therapeutic intervention time: Period in minutes dedicated to therapeutic intervention(s).
- Total small bowel enteroscopy rate: Defined as complete evaluation of the small bowel either with a single approach or combined anterograde and retrograde approach (if complete small bowel enteroscopy is intended anyway (Committee et al. 2015; Gerson et al. 2015).
- Diagnostic Yield (i.e. diagnosis, that explains findings from previous imaging or establishes a new diagnosis, that could explain clinical symptoms, that indicated PSE)
- User feedback and judgment of handling characteristics and other aspects: User feedback and assessment of handling characteristics and other logistical aspects regarding:
 - Handling of PowerSpiral
 - Instrument insertion of PowerSpiral
 - Precision of positioning during therapy of PowerSpiral
 - Time needed for procedure of PowerSpiral
 - Staff and resource needed for procedure of PowerSpiral
- Serious adverse events (PS product related)
- Adverse events during enteroscopy procedure and adverse events (PS product related)

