3.7.2 Adverse Events

The frequencies of adverse events, serious adverse events and device deficiencies will be reported in summary tables. These tables will show the number of subjects per group presenting a (serious) adverse event and the incidence of its occurrence.

Tabulations will be provided for system organ class and stratified by relation to the investigational product. Any withdrawals from the study due to adverse events will be reported. All measures taken due to adverse events will be reported.

AEs of special interest

- Number of patients with pancreatitis
- Number of patients with bleeding
- Number of patients with perforation
- Number of patients with complications associated with sedation/anesthesia
- Number of patients with other complications

For pre-treatment events summary tables and listings will be provided.

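### The primary SAE rate counts events over patients, but the binomial interval and the 8% rule need patients with at least one SAE

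*SAP*

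**What the plan says.** SAP 3.7.1 is the only place that gives the primary rate a numerator and a denominator. The rate "will be computed as the number of such serious adverse events divided by the number of patients in the cSAF". A 95% Clopper-Pearson interval is put on it, two-sided by the default in SAP 3.5. The decision rule appears there and in SAP 2.3: "If the upper confidence limit will be 8% or less, non-inferiority will be concluded".

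SAP 2.4 does not settle the unit: "The rate of serious adverse events during and after enteroscopy will constitute the primary endpoint for this study". The summary tables in SAP 3.7.2 do count people, showing the "number of subjects per group presenting a (serious) adverse event".

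The protocol plans per patient. Table 1 in section 3.3.6 is titled "Precision of estimations of the rate of patients with at least one SAE", and the 8% historical control follows directly below it. Protocol 3.1.3 also expresses its safety endpoint as a percentage and a number of subjects. On repeat exposure, protocol 3.1.2 says: "There may be a second (optional) procedure".

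**The concern.** A Clopper-Pearson interval inverts the binomial distribution. It fits a count of patients who did or did not have an SAE. It does not fit a count of SAEs, because one patient can contribute several: more than one complication of a procedure, or events at both Visit 2 and the optional Visit 3. Nothing in the SAP limits the count to one per patient.

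The non-inferiority rule is the study's only pass/fail decision; protocol 4.1.2 rules out hypothesis testing for efficacy. The direction of the error depends on what the 8% means:

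- **A limit on the proportion of patients.** Extra events can only raise the upper limit, so event counting can turn a pass into a fail and never the reverse.
- **A limit on events per patient.** The binomial interval is too narrow when patients have repeat events, so the chance of wrongly concluding non-inferiority rises.

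The primary rate and the SAE summary table could also show different figures in the same report.

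**Working it through.** **Inputs from the documents.** 260 core patients and 245 analysed (protocol 3.3.6); limit 8%; two-sided 95% interval. The upper limit for x out of n is the 0.975 quantile of Beta(x + 1, n − x). The lower limit is the 0.025 quantile of Beta(x, n − x + 1).

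**Step 1: reproduce Table 1.** With x as patients and n = 245:

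| x | Recomputed 95% CI | Table 1 |
|---|---|---|
| 5 | 0.67–4.70% | 0.7–4.7% |
| 10 | 1.97–7.38% | 2.0–7.4% |
| 15 | 3.47–9.90% | 3.5–9.9% |
| 20 | 5.06–12.33% | 5.1–12.3% |
| 25 | 6.71–14.69% | 6.7–14.7% |
| 30 | 8.42–17.02% | 8.4–17.0% |

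All six rows agree.

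**Step 2: find the cut-off.**

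| n | Largest passing count (upper limit) | Next count (upper limit) |
|---|---|---|
| 245 | 11 (7.89%) | 12 (8.40%) |
| 260 | 12 (7.92%) | 13 (8.40%) |

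Taking 5% off 260 gives 260 × 0.95 = 247 rather than 245; the cut-off is 11 at both.

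**Step 3: same data, two counts.** With n = 245, 11 patients with 12 SAEs pass by patients (7.89%) and fail by events (8.40%). Ten patients with 12 SAEs give 7.38% (pass) and 8.40% (fail).

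**Step 4: how often it matters.** The true SAE rate and the repeat chance are assumptions, not document figures. Let K be the number of patients with an SAE, K ~ Binomial(n, p), and let c be the cut-off.

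- By patients: P(pass) = P(K ≤ c).
- By events: P(pass) = Σ over k ≤ c of P(K = k) × P(further SAEs ≤ c − k, given k).

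Two models were used for further SAEs. In the open-ended model, each SAE is followed by another in the same patient with chance q, so further SAEs given k are negative binomial(k, 1 − q). In the single-repeat model, each affected patient has at most one more, so they are Binomial(k, q).

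| n, true patient rate p | By patients | By events, open-ended, q = 10/20/30% | By events, single repeat, q = 10/20/30% |
|---|---|---|---|
| 260, 3% | 95% | 88/78/65% | 89/82/75% |
| 260, 4% | 76% | 62/48/35% | 64/53/43% |
| 260, 5% | 46% | 33/23/14% | 34/25/18% |
| 245, 4% | 72% | 59/46/33% | 60/50/41% |

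At a 4% rate, the chance that the patient count lands exactly on the cut-off, where one extra SAE reverses the result, is P(K = c): 10% at n = 260 and 11% at n = 245.

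**Step 5: wrongly concluding non-inferiority, n = 260.**

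- True patient rate 8%: 2.3% by patients; 1.2/0.6/0.3% by events (open-ended, q = 10/20/30%).
- 8% read as an event rate, and the true event rate is 8%: 2.3% with no repeats; 3.5/5.2/7.4% (open-ended) or 3.3/4.3/5.2% (single repeat) at q = 10/20/30%, against a nominal 2.5%. Here p is set to 0.08 × (1 − q) in the open-ended model and 0.08/(1 + q) in the single-repeat model.

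**The case against.** The strongest reply is that this is loose drafting. The SAP is based on protocol version 02, which defines safety per subject, and choosing Clopper-Pearson itself presupposes a patient count. That is plausible, but it does not cure the text. SAP 3.7.1 states the numerator explicitly, and a programmer following it would count events. The protocol's per-subject wording shows that the SAP departs from it.

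The second reply concerns direction. The 8% stands directly below a per-patient table, and on that reading event counting cannot produce a false claim of non-inferiority. This stands. The harm is then a lost chance of a correct conclusion, and the raised error rates in step 5 apply only if 8% is an event rate. The documents do not show which unit the cited guideline used.

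Third, the step 4 figures depend on an assumed repeat chance and model. This also stands: at n = 260, a 4% rate and q = 30%, the answer is 35% or 43%. The direction is the same in both, and the cut-offs in step 2 need no assumption.

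Fourth, SAP 3.1 puts every non-training patient with at least one enteroscopy into the cSAF, and protocol 3.1.4 replaces patients who drop out before the procedure. The denominator may therefore be nearer 260 than 245. This is fair, but it only moves the cut-off from 11 to 12.

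**Conclusion.** The concern holds. The primary estimator fits neither its interval nor the quantity the protocol planned, and following the SAP literally can reverse the study's one formal conclusion. That one count decides the result follows from the documents alone. The size of the loss does not: at n = 260 and a 4% patient rate, the chance of passing drops from 76% to between 64% and 35% if repeat SAEs occur with a chance of 10 to 30%. With no repeat SAEs the two definitions coincide and the interval is valid, but the primary analysis should not depend on that.

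A related inconsistency lies in the protocol. Section 3.1.3 says "The main safety endpoint is a combined one, capturing all SAEs / DDs captured during the study period" and then restricts the SAEs to those related to device or procedure. Section 1.2 instead documents all SAEs, "so the overall SAE rate as well as the number of individual types of complications". Table 1 and the first item of section 4.1.3 also point to an all-SAE rate, which the SAP follows. This is a separate, secondary matter.

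**What to change.** In SAP 3.7.1, define the primary rate as the number of cSAF patients with at least one SAE during or after enteroscopy, divided by the number of cSAF patients. Use matching words in SAP 2.3 and 2.4. Keep the Clopper-Pearson interval and the 8% rule on that rate. The chance of passing at a true 8% patient rate is then 2.2% (n = 245) or 2.3% (n = 260), within the nominal 2.5%. Report the total number of SAE events descriptively. Settle the unit before results are known, so that it cannot be chosen at the cut-off.

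Separately, reconcile protocol 3.1.3 with sections 1.2, 3.3.6 and 4.1.3. If the section 3.1.3 endpoint is kept, report it per patient, including device deficiencies, beside the primary rate.

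The cost is one sentence in SAP 3.7.1, matching words in two other sections and at most one extra table row. No new data are needed.

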Endpoints	
 • Diagnostic Yield: Defined as the percentage of procedures that either confirmed a diagnosis from previous studies, or established a new definitive diagnosis at the anatomical location identified in previous studies or findings that could explain the clinical symptoms • Therapeutic Yield: Defined as the percentage of patients with any endoscopic intervention / therapy with the exception of biopsies • Total procedure time: (starting with oral /anal insertion until final withdrawal of the device) • Total therapeutic intervention time • Total small bowel enteroscopy rate: Defined as complete evaluation of the small bowel either with a single approach or combined anterograde and retrograde approach (if complete small bowel enteroscopy is intended anyway) • Endoscopic success rate • Safety: Incidence (% of subjects) and frequency (no. of subjects) with device or procedure related Serious Adverse Events (SAEs) and Device Deficiencies (DD) observed during/after the procedure • User feedback and assessment of handling characteristics of the device
Study Design	International, multicenter, open label, non-randomized, prospective, observational study.
Sample Size	260 subjects will be enrolled into this registry including an expected rate of 5% of losses-to-follow-up during study conduct. The first 5 procedures for each investigator will be performed to get used to the device. Data on these “learning curve” procedures will be captured and analyzed separately. The dataset for final analysis (e.g. procedure time, rate of SAEs etc.) will include 260 cases from procedure #6 onwards in order to account for a learning curve effect. The sponsor plans to activate 12 sites with one or two investigators at each site. Each site shall enroll up to 22 subjects (notwithstanding the learning curve cases) to allow for the same quota per site. Overall approximately 335 subjects will be enrolled (including cases for the learning curve).

Clinical Investigation Plan

CIP Reference No.:2018-GI (OEKG) -01. The **SAMISEN** study - Final Version 02 - Date 23th April 2019

Timelines	Study Start (Enrollment of First Patient) is planned for May/June2019. Enrollment period: 1 year (until May/June 2020). Study closure: Q2/2020.

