1.2 Justification for the Design of the Clinical Investigation

Deep enteroscopy is well established with Balloon assisted enteroscopy procedures, however there is a need for innovative and faster methods, less resource utilization which at the same time provide more comfort for the patients.

Currently available and published data for PowerSpiral was collected by means of Investigator Initiated Trials (Mans et al. 2018; Neuhaus et al. 2016; Beyna et al. 2018; Beyna 2018). With this Olympus sponsored Registry further data about performance and safety for this new medical device will be collected in a larger patient population. Obtained safety data will be compared to data published in respective guidelines or literature.

This study will be performed in parallel to the European market launch of this new medical device. It is a registry study with a CE marked medical device whose application within the intended use will be captured. The registry and does not impose any additional procedure or risk to the patient as we strive to document daily clinical routine. Therefor this study is observational (non-interventional) in nature.

For the same reason inclusion criteria are kept as broad as possible. In summary all patients are eligible where the physician realizes an indication for deep enteroscopy for further diagnostic or therapeutic work up. The exclusion criteria will only affect patients under the age of 18 years and pregnant women. Otherwise clinical judgement of the treating physician is the only relevant and leading reason for exclusion. Of course giving signed informed consent by all study subjects is a prerequisite for participation in this "registry".

For this study approximately 12 European sites will be recruited that offer deep enteroscopy to their patients. This international multi-center setup will give a more representative picture and avoid a single-site bias. Furthermore enrollment will be completed earlier compared to a single center approach.

The prevailing complications of a deep enteroscopy are pancreatitis, perforation, bleeding and adverse events associated with sedation or anesthesia (Aktas et al. 2010; Akarsu et al. 2014; Akerman and Cantero 2009; Arulanandan et al. 2016; He et al. 2013; Moeschler and Mueller 2015). Generally these are independent if the procedure was performed as a diagnostic or therapeutic procedure however the complications rate is usually higher in interventional cases (Rondonotti et al. 2018).

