3.5 Demography, Medical History, Concomitant Medication, Study Procedures

Descriptive statistics (n, mean, standard deviation, median, 25th and 75th percentiles, minimum and maximum) will be calculated for quantitative variables; frequency counts by category will be given for qualitative variables. Confidence intervals will be given where appropriate. If not stated otherwise, these intervals will be two sided in each case and provide 95% confidence. Individual listings will be provided for each parameter examined in this study.

In addition, information on the intervention will be presented as follows:

- Number of patients in whom a complete intervention was planned.
- Number of patients by number of interventions
- Number of patients with complete and incomplete interventions

Intervention

- Were all interventions successfully completed?
- Type of intervention

Intervention time

- Descriptive statistics

Perception of investigator

- Handling of PowerSpiral vs. BAE (worse, similar, better)

Type of sedation

- number of patients with general anaesthesia and sedation

Concomitant medication and medical history will be listed only (if no codes are available).

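### The SAE rate is judged against 8% with an interval that makes no allowance for clustering by site or operator; a small between-site correlation would be enough to push the false-pass risk above the implied 2.5%

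*SAP*

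**What the plan says.** SAP 2.4 sets the endpoint: "The rate of serious adverse events during and after enteroscopy will constitute the primary endpoint for this study". SAP 2.3 sets the rule: "If the upper confidence limit will be 8% or less, non-inferiority will be concluded". SAP 3.7.1 names the method, in the core safety population: "A 95% Clopper-Pearson confidence interval will be computed for the rate to assess the variability of the estimate". The 8% comes from Protocol 3.3.6: "As historical control, a SAE rate of 8% is considered".

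The patients are grouped. The Protocol's trial summary plans 12 sites with one or two investigators each: "Each site shall enroll up to 22 subjects (notwithstanding the learning curve cases) to allow for the same quota per site". Protocol 3.3.6 expects about 15 investigators and adds: "In addition, to reflect the learning curve of each individual investigator, the first 5 patients per investigator will be considered training patients".

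Neither document contains an ICC, a design effect, a site or operator term, or a cluster-adjusted interval. Site and investigator are not among the eight subgroups in SAP 3.3. No summary table listed in SAP 3.9 shows SAEs by site or by investigator; centre appears only as a column in the general listings.

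**The concern.** A Clopper-Pearson interval is exact for independent patients who share one SAE probability. If that probability differs between sites or operators, and these are seen as a sample of the places where the device will be used, the pooled count varies more than the binomial model allows. The computed upper limit then lies too low. The only confirmatory claim in the plan depends on that limit.

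The documents give reasons to think that risk, or its detection, could differ by site:
- Sedation or anaesthesia follows hospital standards (Protocol 1.3), and its complications are of special interest in SAP 3.7.2.
- Lipase and amylase at discharge are recorded only where the hospital measures them routinely (Protocol 3.4.2), so pancreatitis may be found more readily at some sites.
- Contraindications are left to the investigator's judgement (Protocol 3.3.2).

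At stake is a non-inferiority statement that could turn on one or two events, with no summary table to show where the events occurred.

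**Working it through.** **Inputs.** Threshold 8% (SAP 2.3, 3.7.1). 12 sites (trial summary) and about 15 investigators (Protocol 3.3.6). Protocol 3.3.6 expects 245 analysable patients, while the trial summary puts 260 cases in the final dataset; both are used. SAP 3.5 says of its intervals that "these intervals will be two sided in each case and provide 95% confidence", which implies 2.5% in the upper tail; neither document states a type I error. The ICC (ρ) is my assumption, varied from 0 to 0.05.

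**1. The plan's own figures.** With x patients affected out of n, the upper limit is the 97.5% quantile of Beta(x + 1, n − x), and the lower limit is the 2.5% quantile of Beta(x, n − x + 1). For 10/245 this gives 2.0% to 7.4%. All six rows of Protocol Table 1 reproduce.

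**2. The rule without clustering.**
- N = 245: 11 events give an upper limit of 7.89% (pass) and 12 give 8.40% (fail). P(X ≤ 11 | 245, 0.08) = 2.18%.
- N = 260: 12 events give 7.92% (pass) and 13 give 8.40% (fail). P(X ≤ 12 | 260, 0.08) = 2.26%.

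So the rule starts slightly below 2.5%.

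**3. False-pass risk with clustering.** Each cluster's risk is drawn from a beta distribution with mean 0.08 and parameters 0.08(1 − ρ)/ρ and 0.92(1 − ρ)/ρ. Cluster sizes are as equal as possible (N = 260 with 12 sites: 8 of 22 and 4 of 21). The beta-binomial counts are summed exactly.

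| ICC | N=260, 12 sites | N=260, 15 operators | N=245, 12 sites | N=245, 15 operators |
|---|---|---|---|---|
| 0 | 2.26% | 2.26% | 2.18% | 2.18% |
| 0.005 | 2.79% | 2.68% | 2.66% | 2.56% |
| 0.01 | 3.35% | 3.12% | 3.17% | 2.96% |
| 0.02 | 4.51% | 4.02% | 4.24% | 3.79% |
| 0.05 | 8.04% | 6.83% | 7.52% | 6.38% |
| ICC at which risk reaches 2.5% | 0.0023 | 0.0029 | 0.0033 | 0.0042 |

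The crossing point depends on where the whole-number threshold falls. At 260 × 0.95 = 247 patients it is 0.0053 (sites) or 0.0067 (operators).

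For scale, the between-site standard deviation is √(ρ × 0.08 × 0.92). That is 1.3 percentage points at ρ = 0.0023, 2.7 at 0.01 and 6.1 at 0.05.

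**4. Effect on a borderline result.** DE = 1 + (m − 1)ρ with m = 260/12 = 21.67, and the exact limit is recomputed on x/DE and N/DE. For 12/260:
- ρ = 0.01: DE = 1 + 20.67 × 0.01 = 1.207, so 9.94 events in 215.5 patients; upper limit 8.34%.
- ρ = 0.02: DE = 1.413, so 8.49 events in 184.0 patients; upper limit 8.73%.

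The planned limit is 7.92%, so either value reverses the verdict. For 11/245 the limits are 8.29% and 8.68%, against 7.89%.

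**5. Sites as fixed strata.** With half the sites at 4% and half at 12% (mean 8%, N = 260), the exact pass probability is 2.15%. With 2% and 14% it is 2.02%. Neither exceeds the 2.26% under a common rate.

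**6. Price of an adjusted limit.** I simulated 200,000 trials with N = 260, 12 sites, no clustering and a true rate of 4%, using the estimator given under the fix. The estimated design effect runs from about 0.5 to 1.8 (5th to 95th percentile). The planned rule passes 75.8% of trials; a rule based on the adjusted limit, with the design effect floored at 1, passes 67.4%.

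**The case against.** A reader might infer that the planned limit is too low as a matter of fact and that the false-pass risk does exceed 2.5%. The documents do not support that. They give no ICC, the exact risk starts below 2.5%, and step 5 shows no inflation if the sites are regarded as fixed strata with fixed quotas. The choice between fixed and random sites belongs to the definition of what is being estimated, and the plan does not make it. This part of the objection stands. The stated purpose nevertheless leans towards random sites: the trial summary speaks of daily medical practice, SAP 3.7.1 draws a conclusion about the device against earlier balloon systems, and Protocol 1.2 says "This international multi-center setup will give a more representative picture and avoid a single-site bias".

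It is also tempting to read the run-in as an admission that operators differ. It concerns each operator's growing experience. Removing those cases, together with the required experience and training (Protocol 1.1), should reduce later differences. The single-site remark likewise describes a safeguard and does not assume correlated risk.

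Nor would a cluster of events be hidden. The listings carry centre, and about 12 events can be counted by hand. What is missing is a prespecified summary.

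Finally, SAP 3.7.1 divides the number of SAEs by the number of patients, whereas the calculation here, like Protocol Table 1, counts patients with at least one SAE. Repeat events would raise the rate and work against a false pass. Clopper-Pearson is valid only for the patient count.

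**Conclusion.** The concern holds in conditional form. The plan makes no allowance for clustering by site or operator. If SAE risk varies between them and the conclusion is meant to extend beyond them, the upper limit is too low. With 12 sites, an ICC of roughly 0.0023 (N = 260) to 0.0033 (N = 245) is enough to take the false-pass risk past the implied 2.5%, and an ICC of 0.01 to 0.05 takes it to about 3% to 8%. With 15 operators the effect is somewhat smaller.

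This rests on near-equal clusters, one level of clustering at a time, a beta distribution of risks and an assumed ICC range. Unequal cluster sizes would raise the design effect.

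A further inference, that the adjusted limit should replace the primary rule, does not follow. With about 12 events the design effect is poorly estimated, and step 6 shows the loss of power when there is no clustering at all. A sensitivity analysis is the proportionate response.

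**What to change.** In SAP 3.7.1:

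1. Keep the Clopper-Pearson limit as the primary rule, and define the numerator as patients with at least one SAE.
2. Add a named sensitivity analysis: an exact upper limit computed on x/DE and N/DE with site as the cluster. For k sites with m_j patients and y_j affected, and p = x/N, estimate DE = [k/(k − 1) × Σ(y_j − p·m_j)²/N²] / [p(1 − p)/N]. Set DE to 1 if the estimate is smaller or if there are no events.
3. State that, if the primary rule passes but this limit exceeds 8%, the non-inferiority conclusion will be reported as not robust to site clustering.

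In SAP 3.9, add a summary table of patients with an SAE by site and by investigator, with denominators.

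The cost is SAP wording and a few lines of code. No new data are needed: centre is already in the listings, and Protocol 3.4.2 records the investigator who performs each procedure. The drawback is occasional false alarms. In step 6, with no clustering, (75.8 − 67.4)/75.8 = 11% of passing trials would carry the qualification by chance. The report should give the estimated design effect and say that it is imprecise.
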